This study proposal focusing on patient-provider symptom communication in advanced cancer population is a groundbreaking study which addresses **not only an underexplored area in Taiwan but also two global research priorities in Cancer and Palliative Care: symptom management and communication (51-56)**. For instance, the 2014–2018 Oncology Nursing Society (ONS) Research Agenda Project Team identified eight high-priority cancer research areas including symptoms. Since 2001, managing physical and psychological symptoms in patients with cancer has consistently topped the ONS Research Agenda. The ONS Research Agenda Project Team also pointed out that studies enhancing communication in palliative care are a priority area for research (51, 52). Likewise, research focusing on using symptom management to improve HRQOL for patients with cancer has been a focus for National Institute for Nursing Research (NINR) for over 25 years. NINR has also stressed the importance of establishing effective patient—provider communication in order to promote health and decision-making regarding complex treatment and care options, especially in end-of-life care (54). In a European survey which obtained researchers' opinions from 36 countries found that symptom management, especially pain, was rated as the most active and most important research area in cancer end-of-life care (56). On the other hand, the quality of patient—provider communication is questionable and may link to several health issues, including patient outcomes, in Taiwan. Grounding on international evidence, this proposed study is a critical step to close knowledge gaps of symptom communication and management and identify local problems. Findings will inform relevant research, education, and clinical practice in Taiwan. Moreover, our findings will serve as a basis to transform healthcare in Taiwan by raising public awareness and facilitating expert discussions of issues related to patient—provider communication.

Conflict of Interest

The researchers declare that they have no conflict of interest. The research and development results ownership belongs to National Taiwan University.

Privacy and Confidentiality

All data will be de-identified by using heuristic methods. Electronic data will only be send using NTU or NTUH email system and be stored in the secure space at the network-attached storage system which can only be accessed with assigned username and password. Written information will be locked in PI's office at National Taiwan University.

	Year	2018		2019				2020				2021	
	Months	9	10-12	1-3	4-6	7-9	10-12	1-3	4-6	7-9	10-12	1-3	4-7
Phase 0. Obtain IRB approval		x											
Phase 0. Obtain questionnaire measurements		x											
Phase 0. Establish research team		x											
Phase 0. Recruit oncologists & patients			x	x	x								
Phase 1. Record 1 OPD visit & collect questionnaire measurements			x	x	x								
Phase 1. Interview				x	x	x							
Phase 1. Analyze recorded office visits					x	x	x	x	x				
Phase 1. Analyze interviews					x	x	x	x	x				
Phase 1. Check study trustworthiness: request selected participants' feedback on qualitative results									x	x			
Phase 2. Analyze quantitative data based on qualitative findings of recorded OPD visit									x	x	x		
Phase 2. Compare the qualitative findings of interview with the quantitative data (triangulation)										x	x	x	
Phase 2. Check study trustworthiness: request international experts' feedback on final results												x	
Phase 2. Report and Manuscript writing												x	x

*Abbreviation: Out-patient-department (OPD)

	Expecting direct research results	Expecting indirect process results
YEAR 1 (2018, 9—2019, 7)	
 ▪ Obtaining IRB approval ▪ Obtaining questionnaire measurements ▪ Finishing the recruitment of oncologists and patients 	
 ▪ Establishing research team: recruit members and establish regular meetings ▪ Training: recruitment strategies and research methodology (mixed-methods), interview skills ▪ Presenting methodology at local/national/international conferences ▪ Online international collaboration: study design
YEAR 2	
 ▪ Finishing collection of qualitative data: recorded 	
 ▪ Identifying and securing international collaboration opportunities

(2019, 8—2020, 7)	
office visits & interviews
 
 ▪ Finishing collection of quantitative data: questionnaire measurements 	
 ▪ Training: data collection (qualitative and quantitative) and data analysis (discourse analysis method, content analysis method, usage of Nvivo) ▪ Presenting recruitment process and results at local/national/international conferences ▪ Online international collaboration: ensure study trustworthiness
YEAR 3 (2020, 8—2021, 7)	
 ▪ Completing the analysis of qualitative data: recorded office visits & interviews ▪ Completing the analysis of quantitative data: questionnaire measurements ▪ Triangulation 	
 ▪ Continuing international collaboration through on-site visits and email or online discussions ▪ Identifying conferences and journals for results dissemination ▪ Presenting preliminary results at local/national/international conferences ▪ Training: data analysis (descriptive and correlational statistics, triangulation, usage of SPSS) ▪ Onsite international collaboration: ensure study trustworthiness

Table 5. Practical Results				
		9, 2018—7,2019	8, 2019—7,2020	8, 2020—7,2021
Manuscripts	Journal	1 (methodology)	2 (discourse analysis results, content analysis results for patient)	3 (content analysis results for caregiver, quantitative results for patient and caregiver)
	Conference	1	2	3
Research Reports		1	1	1

References

1. van Osch M, van Dulmen S, van Vliet L, Bensing J. Specifying the effects of physician's communication on patients' outcomes: A randomised controlled trial. *Patient education and counseling*. 2017.

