1. Validate TIPSC in Taiwanese advanced cancer population in terms of how patients, caregivers, and HCP discuss symptoms during out-patient-department (OPD) visits.
2. Explore patients’/caregivers’ experience and thoughts of symptom discussion in regard to their interaction patterns and symptom experience.
3. Examine relationships between interaction patterns and (a) demographic variables: age and educational level, (b) symptom severity, (c) congruence in symptom assessment between patients/caregivers and HCP, (4) patients’/caregivers’ perceived ability to communicate with

HCP, and (5) patient/caregiver satisfaction.

Conceptual Underpinnings

The specific aims and research design of this proposed study are informed by two conceptual frameworks. **Aim one and two which seek to deductively explore interaction patterns of symptom communication are informed by a typology, TIPSC, developed by the applicant.** The applicant used qualitative methods to explore naturally occurring symptom discussions to establish this typology that describes eight interaction patterns of advanced cancer patient—provider symptom communication. These eight interaction patterns which reflects unique style of symptom communication are collaborative, explanatory, agentic, checklist, cross-purpose, empathic, admonishing, and diverging interactions (24). The definitions and exemplars of each interaction pattern are presented in table 1. Building on this typology developed in the U.S., the proposed study seeks to explore and categorize symptom communication in Taiwanese cancer population and, at the same time, verify or even expand the TIPSC. Once the qualitative verification of the TIPSC is established, we are able to quantitatively examine the relationship between interaction patterns and meaningful variables or outcomes which lead to our specific aim three.

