Aim 1. Validating a newly established typology regarding interaction patterns of unstructured symptom discussion in Taiwanese advanced cancer population.

Aim 2: Exploring patients’ experience and thoughts of symptom discussion in regard to their interaction patterns and symptom experience.

Aim 3: Examine relationships between interaction patterns and (a) demographic variables, (b) symptom severity, (c) congruence in symptom assessment between patients/caregivers and providers, (d) patients’/caregivers’ perceived ability to communicate with providers, and (e) patient/caregiver satisfaction.

Procedures

- Recruiting oncologists, patients, and caregivers (collecting demographic information and scheduling an out-patient-department (OPD) visit to be recorded)
- Record 1 OPD visit
- Collect quantitative data: questionnaire measurements
- Schedule an 30-40 minutes interview
- Interview (Incentive will be provided after the interview)
- Analyze the recorded office visit using discourse and conversational analysis: determining interaction patterns
- Analyze the interview using content analysis: exploring patients’ experience regarding the recorded symptom communication
- Analyze quantitative data: the relationship between identified interaction patterns and questionnaire measurements
- Triangulation: compare the results from qualitative interview with the quantitative data to see how the data support or disagree with each other
- Drafting preliminary research report

Figure 2. Research Schema: Conceptual Underpinnings, Study Phases, and Corresponding Specific Aims and Procedures

Methods and Procedures

The method section describes sampling process and study methods of each phase.

Sampling. Because a qualitative study typically requires about 30-50 participants (28), the sample size of this pilot study is set to be 50. The two samples of phase one and two will include the exactly same individuals and same sample size which is about **50 patient/caregiver—physician dyads**, including about 50 patients, 10 physicians, and 50 caregivers, if applicable.

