There are three steps of recruitment processes. First, physicians who are currently in clinical practice at National Taiwan University Hospital and care for patients with solid tumors will be recruited through study presentations at grand rounds, meetings, or personal contacts. A research assistant then meets with interested physicians for explaining the details of the study, consenting, and setting up following schedules for recruiting patients at OPD visits. Second, research assistants identify potential eligible patients by working closely with participating physicians and their clinic nurses. These potential eligible patients will be approached by their physicians, nurses, or research assistants. We include patients who are: (1) currently a patient of a participating physician, (2) diagnosed with advanced solid cancer (TNM stage III or IV), (3) aged 20 years or older, (4) able to tolerate an interview that will last approximately 30 minutes, and (5) able to speak Chinese or Taiwanese. Patients who (1) do not experience any symptoms, or (2) are hospitalized at recruitment are excluded. Finally, caregivers who will participate in the OPD visits with participating patient will be approached. Caregivers who are younger than 20 years old or cannot speak Chinese or Taiwanese will be excluded.

Recruitment process. Interested patients and their caregivers will receive a pamphlet regarding study information when research assistants explain study process, confirm participation, and arrange schedules. Signed written consents will be obtained from physicians, patients, and caregivers before data collection. Participated patients and caregivers are required to (1) provide an audio-recorded, unstructured OPD visit with their physicians, (2) complete 3 survey measurements (European Organization for Research and Treatment of Cancer, Perceived Efficacy in Patient-Physician Interactions scale, and The Chinese Patients' Satisfaction Scale), and (3) participate in a 30-40 minutes interview at home or a private room. On the other hand, participated physicians will complete European Organization for Research and Treatment of Cancer immediately after the recorded OPD visit. Figure 3 represents the recruitment and data collection process.

[figure not shown]

Fig 3. Recruitment and Data Collection Process

Table 2. Example Interview Guide (Patient version)

*[] 中文字會視每位病人在診間與醫師的對話內容而更動

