Our study faces several possible challenges including the difficulties of recruiting physicians and advanced cancer patients because of physicians' limited time and the critical condition of patients with advanced cancer. Strategies designed to tackle these challenges including closely working with clinical experts, allowing reasonable recruitment duration, providing incentives, and interviewing patients/caregivers at a place of their choice.

Expecting Results

This will be a three-year study project starting from September, 2018. Table 3 shows study procedure and timeline. The expecting results of the research projects can be discussed in two categories: direct research results and indirect process results (table 4). The major **direct research results are: (1) the verified TIPSC and (2) a comprehensive map describing symptom communication including interaction patterns and associating factors.** The major **indirect process results which are the byproducts of the proposed research include (1) parameters establishment for larger scale quantitative studies, (2) establishment of a health communication lab, (3) international and interdisciplinary collaboration, and (4) international/national/ local conference presentations and journal publications** (i.e. practical results). The next paragraph describes the corresponding resources and strategies of achieving these indirect process results.

Parameters establishment for larger scale quantitative studies. As this pilot study is among the first to describe the relationship between interaction patterns and clinical outcomes, our findings can be used to calculate power and determine adequate sample sizes for future, larger scale quantitative studies.

Establishment of a health communication lab. The specific plan is to (1) conduct informational interviews in the campus with colleagues and students about suggestions and resources of beginning a lab, (2) recruit research team members and create training plans, (3) establish the lab culture and routines, such as missions, equipment and space, website, lab management systems, and regular meetings, (4) identify and securing collaboration opportunities by promoting the lab and research at research meetings and conferences, (5) networking other similar labs in Taiwan (e.g., language and communication lab at National Cheng Kung University) and other countries.

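### Participating physicians help choose, and may themselves approach, the patients whose visits are recorded, and no rule governs selection, so strained interactions could be under-represented without anyone being able to tell

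*Combined protocol and SAP*

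**What the plan says.** The recruitment steps are under Methods and Procedures, Sampling. Physicians come first: they "will be recruited through study presentations at grand rounds, meetings, or personal contacts". For patients, "research assistants identify potential eligible patients by working closely with participating physicians and their clinic nurses", and then: "These potential eligible patients will be approached by their physicians, nurses, or research assistants". The text does not say who makes the approach in which case.

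The inclusion criteria begin with being "currently a patient of a participating physician". The others are stage, age, ability to tolerate the interview and language. Patients who "do not experience any symptoms, or (2) are hospitalized at recruitment are excluded". None of these criteria concerns how patient and physician get on.

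On size, "the sample size of this pilot study is set to be 50", with about 10 physicians. The same people serve both phases.

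The recorded visits are sorted by a typology of eight patterns: "collaborative, explanatory, agentic, checklist, cross-purpose, empathic, admonishing, and diverging interactions" (Conceptual Underpinnings). Expecting Results promises "a comprehensive map describing symptom communication including interaction patterns and associating factors".

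**The concern.** The people whose conversation is analysed have a hand in deciding which of their conversations are analysed. Physician behaviour is part of the coding. Step 6 of the Phase 1 analysis, for example, recognises the checklist pattern by the way the provider asks questions. A physician who suggests a cooperative patient in a busy clinic is enough to tilt the sample; bad faith is not needed. Every patient passed over may still meet all the criteria, so nothing in the study record would show it.

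Aim 1 asks whether the eight patterns hold in Taiwanese patients. That does not need a representative sample, but it does need the range of patterns to have a chance to appear. If difficult interactions are put forward less often, a rare or missing pattern has two explanations, population and selection, and the data cannot separate them. Aim 3 uses the same dyads, so selection related to rapport could also narrow the spread of patterns and satisfaction in the regressions. The project further intends its results to supply power calculations for larger studies (Expecting Results), and these would inherit any such narrowing.

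**Working it through.** **1. What the text allows, and what limits it.**

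- Identification: research assistants, jointly with physicians and clinic nurses.
- Approach: physician, nurse or research assistant, with no allocation rule.
- Choice among eligible patients: no consecutive, random or purposive rule was found.
- Record of selection: no screening log was found, and no count of eligible patients not approached or declining.
- Trustworthiness section: documentation, team meetings, peer and participant feedback, description of context, and expert review. None of these controls who is recorded.
- Innovations and Challenges: the recruitment strategies concern clinical contacts, time, incentives and interview location, not selection.

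**2. The plan's own figure.** The sample of 50 comes from a customary range of 30 to 50 for qualitative studies. It has no formula behind it, so there is nothing to reproduce. With about 10 physicians, 50 / 10 = 5 patients each on average, so one physician's choices can shape about a tenth of the sample.

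**3. Illustration of size.** Neither input below is in the documents; both are assumptions.

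- p: share of eligible visits showing a given difficult pattern.
- s: chance that such a patient is put forward, relative to other patients.
- Share among recorded visits: q = p·s / (p·s + 1 − p).
- Expected visits with the pattern: 50q.
- Chance of at least one: 1 − (1 − q)^50. The chance of at least three is the binomial tail with n = 50.

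Example: for p = 0.06 and s = 0.5, q = 0.03 / (0.03 + 0.94) = 0.0309, and 1 − (1 − 0.0309)^50 = 0.792.

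| p | s | q | Expected visits | At least one | At least three |
|---|---|---|---|---|---|
| 0.02 | 1 | 0.0200 | 1.00 | 0.636 | 0.078 |
| 0.02 | 0.5 | 0.0101 | 0.51 | 0.398 | 0.014 |
| 0.04 | 1 | 0.0400 | 2.00 | 0.870 | 0.323 |
| 0.04 | 0.5 | 0.0204 | 1.02 | 0.643 | 0.082 |
| 0.06 | 1 | 0.0600 | 3.00 | 0.955 | 0.584 |
| 0.06 | 0.5 | 0.0309 | 1.55 | 0.792 | 0.201 |
| 0.10 | 1 | 0.1000 | 5.00 | 0.995 | 0.888 |
| 0.10 | 0.5 | 0.0526 | 2.63 | 0.933 | 0.494 |
| 0.10 | 0.25 | 0.0270 | 1.35 | 0.746 | 0.153 |

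(The 0.955 is 95.47% before rounding, so 95%.)

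A pattern in a tenth of visits would usually still be seen once. The chance of the several examples needed to refine a definition, or to support a dummy variable in Phase 2, falls more steeply: from 0.888 to 0.494 at s = 0.5.

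**4. Sensitivity to one pattern per visit.** The table counts one pattern per visit, but the Phase 2 analysis text allows combinations. Suppose instead three independent symptom exchanges per visit, or 150 units (also an assumption), with the pattern's share halved from 3% to 1.5%:

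- 50 units: 1 − 0.97^50 = 78% falls to 1 − 0.985^50 = 53%, a loss of about 25 points.
- 150 units: 1 − 0.97^150 = 99% falls to 1 − 0.985^150 = 90%, a loss of about 9 points.

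Exchanges within one visit are likely to be correlated, which would put the answer between these two cases. The losses in the table are therefore probably at the upper end. Clustering within physicians is ignored, as is the rule that only visits with symptom talk are analysed.

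**The case against.** The strongest reply is that the plan is a descriptive qualitative pilot and the mechanism is conjecture. Several parts of that reply stand.

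- Research assistants are the named identifiers and one of three possible approachers. They also explain the study and confirm participation, and written consent comes before data collection. The physician is not the sole gatekeeper.
- A reader might infer that physicians know their talk may be labelled admonishing or diverging, and so have a motive to steer. The typology is set out for readers of the proposal. The Sampling text says only that the study is explained to physicians, not that they are told the labels. Nor does the study rate physicians; it treats talk as jointly produced.
- A reader might infer that an unobserved pattern would be dropped from the typology. No such rule appears: the plan speaks of verifying, refining and possibly expanding it.
- A reader might infer that patients are selected on satisfaction or congruence. Neither is known at recruitment. Congruence needs the physician's rating, which is made after the recorded visit. Any selection on these would be indirect, through rapport.
- Transferability is handled by describing the context and leaving applicability to readers, which is normal for qualitative work. Purposive maximum-variation sampling would be as legitimate as consecutive approach.

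What the reply does not remove is that neither kind of rule is stated. Describing the context does not reveal who was passed over, and the Research Design section does state an aim to generalise. Figure 3, on recruitment, was not readable in the text used here. If it sets a selection rule, the point narrows accordingly.

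**Conclusion.** The point holds as a weakness of procedure, not as a demonstrated bias. Physicians whose talk is coded may influence which of their patients are recorded, with no rule for choosing among eligible patients and no record from which selection could be judged. The consequence is loss of interpretability in aim 1 and a possible narrowing of patterns and satisfaction in aim 3.

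Its size cannot be estimated from the documents. The probabilities above rest on assumed prevalences, an assumed strength of selection and one pattern per visit, and they probably overstate the loss. Thinning of an uncommon pattern is more plausible than its disappearance. It would go too far to conclude that steering will occur, that physicians are selecting on the outcomes, or that the typology's validation is invalid. The change is worth making because it is cheap and needs no change in sample size or staff.

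**What to change.** Amend the recruitment text under Sampling as follows.

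- On recruitment days, the research assistants already in the plan screen each participating physician's outpatient list against the stated criteria and approach eligible patients consecutively. If the team prefers purposive sampling for range, it should state that rule in advance and keep the same log.
- Physicians and nurses only confirm eligibility. Any objection to approaching a patient is logged with its reason.
- The treating physician does not make the approach.
- The report gives, by physician, the numbers eligible, objected to, declined and recorded.
- The report states as a limitation that the physicians are themselves volunteers, some reached through personal contacts. Consecutive approach does not cure that earlier selection step.

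The cost is one amended paragraph, a screening log, and possibly a higher refusal rate than when the physician asks.

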While the proposed study does not intend to test the whole theory, specific aim three was informed by the Dual Process Theory of Supportive Message (DPT). DPT was firstly published by Burlison in 2008 with the main purpose of providing a systematic explanation about factors affecting communication and its outcomes (25). One of the important assumptions proposed by the DPT is: communicators' ability to handle the message (A) and their motivation (M) to discuss the topics mediates the relationship between quality of communication (Q) and communication outcomes (O). In the proposed study, we conceptualize the 'ability to handle the message' as **patients' perceived ability to communicate with providers** and 'motivation' as **symptom severity**. That is, we propose to explore the relationship between **TIPSC (Q)**, **patients' perceived ability to communicate with providers (A)**, **symptom severity (M)**, **congruence in symptom assessment between patients and providers (O)**, and **patient satisfaction (O)**. Figure 1 shows the modified conceptual framework.

[figure not shown]

Figure 1. Modified Conceptual Framework of Dual Process Theory of Supportive Message

Table 1. Interaction Patterns, Defining Characteristics, and Exemplars

Interaction pattern	Defining characteristics	Exemplars [O] Oncologist, [P] Patient, [C] Caregiver

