今天的會談主要想了解您對於上次在診間、被錄音的那次會診的想法或感受。我們的重點尤其會放在當時您在診間溝通症狀時的一些內容；等一下我所問的問題都沒有所謂的正確答案，主要是以您的感覺為主。在開始之前，我很樂意回答您的任何問題。

1. 請回憶上次的會診，您在開始與醫師談話前是否有特別想討論的重點或問題？
2. 告訴我您對這次與醫師談話的任何感受、感想或印象最深刻的的事情。
3. 您與醫師曾討論[所有在診間討論提及的症狀]，請以你的話描述一下當時討論這些症狀的情形。
4. 在討論這些症狀的當下，您的感受是...？
5. 請問您當時還有任何症狀或問題是沒有被提及的嗎？為什麼？請多跟我描述這個[症狀或問題]。
6. 我們發現，您和醫師常以[以簡易方式說明某種互動模式]討論症狀，對於這種互動模式，您的想法或感受是...？
7. 依您的看法，這次的診間談話與平常的診間談話比較起來...？
8. 您覺得這次的談話有什麼優點或是可以改進的地方？

Phase 1: qualitative data collection and analysis. The qualitative phase is a qualitative descriptive study because we want to provide a fundamental and straightforward description regarding the validation of TIPSC (aim 1) and how patients experience and think about the interaction (aim 2).

On the day of the scheduled, audio-recorded office visit, a research assistant will first meet with the patient and caregiver for completing the survey measurements and then accompany them to the office, set up the recording device, and leave. The research assistant will collect the device and recordings after the visit and schedule a follow-up interview between 2 days to a week after the recorded visit. This 30-40 minutes follow-up interview will be conducted by the PI who is a certified oncology nurse with expertise in qualitative study, symptom management, and psycho-oncology. The PI will listen to the recorded visit before interviewing each patient in order to design individual-specific interview questions. Table 2 demonstrates example interview guide. All recorded visits and interviews will be transcribed verbatim.

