In addition to demographic information, three questionnaire measurements: **European Organization for Research and Treatment of Cancer (EORTC-QLQ C30)**, **Perceived Efficacy in Patient-Physician Interactions scale (PEPPI)**, and **The Chinese Patients' Satisfaction Scale (C-PSS)** will be used to collect data regarding symptom severity, perceived ability to process the information, and overall satisfaction, respectively. The oncologists are required to provide their own demographic information and EORTC-QLQ ratings after seeing each participated patient. Patients are required to provide information of demographic data, EORTC-QLQ C30, PEPPI, and Satisfaction scale. The demographic information will be collected at the time of recruitment while other questionnaires will be collected after the recorded office visits. More information regarding each questionnaire measurements are described below.

Symptom severity will be measured by **European Organization for Research and Treatment of Cancer (EORTC-QLQ C30, Taiwan Chinese version)**. The EORTC QLQ-C30 is a 30-item questionnaire developed by a group of scientists to evaluate functions, symptoms, and overall health-related quality of life of cancer patients. EORTC QLQ-C30 has been verified and widely applied in health-related research. Evaluators rate patients' functions, symptoms, and quality of life using 4-point Likert scales. The Taiwan Chinese version of the EORTC QLQ-C30 has been tested and shows good reliability and validity (43, 44). The reported Cronbach's alpha coefficient of most items was above 0.70 across studies. A 5-10—points difference of EORTC QLQ-C30 rating is considered a significant difference (45). That is, if the difference of EORTC QLQ-C30 rating between a patient/caregiver and a physician is greater than 5, it is defined as an incongruence symptom report.

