Patients' perceived ability to communicate with providers will be measured by **Perceived Efficacy in Patient-Physician Interactions Scales (PEPPI-10, Chinese version)**. PEPPI-10 is a self-evaluated, 10-item instrument measuring patients' self-efficacy in "obtaining medical information and attention to their medical concerns from physicians (46)." Patients rate their confidence of interacting with physicians (e.g., get a doctor to pay attention to what you have to say) from "no confident (0)" to "extremely confident (10)". The Chinese version of PEPPI-10 shows good validity and reliability with the reported Cronbach's α coefficient of 0.907 (47).

Patients' overall satisfaction will be measured by the **Chinese Patients' Satisfaction Scale (C-PSS)**. C-PSS is a 27-item instrument which was developed to measure Chinese patients' satisfaction using a 5-point Likert scale. Patients rate their satisfaction from strongly disagree (1) to strongly agree (5) with higher scores represent better satisfaction. It is a reliable and valid tool with the reported Cronbach's alpha coefficient of all dimensions above 0.90 (48).

The major interaction patterns or combination of interaction patterns will be determined and dummy coded. Binomial Logistic Regression will be used to examine the relationship between interaction patterns and dichotomous variables (i.e., the congruence of symptom reports) while Linear Regression will be applied to examine the relationship between the interaction patterns and other variables, such as age, level of symptom severity, perceived communication ability, and satisfaction. The SPSS software will be used to organize the data and facilitate data analysis. Finally, combining and comparing the findings from the interviews and the results from the quantitative measurements enable us to do triangulation to fully map up the interaction behavior pertinent to symptom discussion.

Trustworthiness

To ensure the quality of study results and conclusions, five standards outlined by Miles and colleagues (2013) will serve as an evaluative framework. The standards are **confirmability, reliability, credibility, transferability, and utilization**.

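### The plan places the patient questionnaires both before and after the recorded visit; in the pre-visit order, satisfaction is scored before the interaction it is analysed against

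*Combined protocol and SAP*

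**What the plan says.** Four places bear on when patients and caregivers complete the questionnaires.

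- **Phase 1: qualitative data collection and analysis.** On the visit day "a research assistant will first meet with the patient and caregiver for completing the survey measurements and then accompany them to the office". The assistant then sets up the recorder and leaves. Afterwards the assistant retrieves the device and recordings and books the interview; no questionnaire step is listed after the visit.
- **Phase 2: Quantitative data collection and analysis.** "The demographic information will be collected at the time of recruitment while other questionnaires will be collected after the recorded office visits".
- **Figure 2, Procedures.** The step "Collect quantitative data: questionnaire measurements" comes directly after the step for recording the visit.
- **Recruitment process.** Participants must "complete 3 survey measurements (European Organization for Research and Treatment of Cancer, Perceived Efficacy in Patient-Physician Interactions scale" and the C-PSS). These are numbered after the recorded visit and before the interview. Physicians complete their EORTC rating immediately after the visit.

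On use of the data, Conceptual Underpinnings labels interaction patterns as quality of communication (Q), perceived ability as A, symptom severity as M, and both congruence and patient satisfaction as outcomes (O). The Phase 2 section relates satisfaction to the coded patterns by linear regression and congruence by binomial logistic regression. A patient–physician difference that "is greater than 5, it is defined as an incongruence symptom report".

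**The concern.** The Phase 1 and Phase 2 sentences give opposite orders for a single administration. If staff follow Phase 1, three things result.

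1. **Satisfaction.** The C-PSS is scored before the interaction pattern it is related to. An association could reflect existing satisfaction or earlier visits with the same physician, but not an effect of the recorded visit. Aim 3 is correlational, so the association could still be examined, but the outcome role given to satisfaction in the framework would be lost.
2. **Congruence.** The patient rates symptoms before the discussion and the physician after it. The greater-than-5 rule could then mix true disagreement with change over the visit.
3. **The recorded talk.** Completing a symptom questionnaire just before the visit may prompt discussion that is later analysed as naturally occurring. This is only a possibility, and interview question 7, which asks how the visit compared with usual ones, is a partial check.

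If some staff follow one section and some the other, questionnaire timing becomes an unrecorded difference between patients. No later analysis could adjust for it.

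**Working it through.** No formula applies, and the plan gives no figure to reproduce. The check is to set the statements side by side.

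| Source | Order given | How explicit |
|---|---|---|
| Phase 1 text | questionnaires, visit, interview | stated |
| Phase 2 text | visit, then questionnaires | stated |
| Figure 2, Procedures | visit, questionnaires, interview | list position only |
| Recruitment process | visit, questionnaires, interview | numbered requirements, not a schedule |
| Timeline table | recording and questionnaires share one row | does not settle it |
| Figure 3 | not visible in the text reviewed | could not be checked |

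**Can the two explicit statements be reconciled?**

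- The Phase 1 phrase might mean only the demographic form. It does not: Figure 2 and the Phase 2 text both collect demographics at recruitment, and the Recruitment process paragraph uses the same term for the three instruments. That all three are meant is an inference from reading the two paragraphs together, but no other reading fits.
- Forms might be completed before the visit and only picked up after it. The Phase 1 text lists only the device and recordings for pick-up, and the Phase 2 sentence uses the same verb for demographics, where it means obtaining the data.

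**Extent of the conflict.** The aim 3 relationships are:

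- (a) demographics: one consistent time, at recruitment
- (b) severity: QLQ-C30, conflicting
- (c) congruence: patient against physician QLQ-C30, with the patient side conflicting
- (d) perceived ability: PEPPI, conflicting
- (e) satisfaction: C-PSS, conflicting

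That is 4 of 5 relationships and 3 of 3 instruments.

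**Post-visit burden.** If all three follow the visit: 30 (QLQ-C30) + 10 (PEPPI) + 27 (C-PSS) = 67 items. If only the C-PSS does: 27 items.

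**Which order fits each instrument's role?**

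- C-PSS is an outcome, so it belongs after the visit.
- QLQ-C30 serves two roles. As severity (M), a post-visit score could be altered by the visit. As one half of congruence, a pre-visit score is not taken at the same point as the physician's rating.
- PEPPI (A) could likewise be altered by the visit if measured after it.

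So the C-PSS has a clear answer, while the other two need a deliberate choice.

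**The case against.** The strongest reply accepts the contradiction and disputes what follows from it.

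- **Only two places state an order outright, one each way.** Figure 2 implies order by list position, and Figure 3 may settle the matter. This stands as a limit on calling the Phase 1 sentence the odd one out. It does not remove the conflict.
- **The plan says patients' "overall satisfaction will be measured by the" C-PSS, without tying the scale to the recorded visit.** Patients are already under the participating physician, so a post-visit score would also carry earlier experience. This stands: moving the C-PSS restores temporal order but does not isolate an effect of the visit. A pre-visit score, however, cannot reflect the visit at all.
- **The 4-of-5 count measures exposure to the wording, not harm.** This also stands. The clear harm is to satisfaction, with possible harm to congruence. Severity and ability are not outcomes in the framework.
- **Change in scores over one visit, and priming, are conjecture.** Agreed; nothing in the documents shows either, and the conclusion does not depend on them.
- **Correcting one Phase 1 sentence would end the contradiction.** True. Stating a reason for QLQ-C30 and PEPPI timing, and recording completion times, goes beyond the minimum. Both are worthwhile because each order has a cost for those two scales.
- **Caregivers may not be affected.** The Phase 2 list of who completes what names oncologists and patients only, whereas the Recruitment process and Phase 1 text include caregivers. The caregiver count is therefore an upper limit.

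**Conclusion.** The concern holds. The plan gives two incompatible times for the patient questionnaires, and nothing visible resolves them. The conflict reaches 3 of 3 instruments, 4 of 5 aim 3 relationships, about 50 patients and at most 50 caregivers. Followed as written, the Phase 1 order measures one of the framework's two outcomes (satisfaction) before its supposed antecedent. It also compares ratings from either side of the discussion for the other outcome (congruence).

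This rests on two assumptions: that the Phase 1 term covers the three instruments named under Recruitment process, and that Figure 3, which could not be seen, does not settle the order. The direction and size of any bias cannot be derived from the documents, and none is claimed. The point should be fixed. It does not invalidate the study, but it costs almost nothing to correct before data collection and cannot be corrected in analysis afterwards.

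**What to change.** 1. Rewrite the Phase 1 sentence so that the C-PSS is completed after the recorded visit, when the research assistant returns for the recorder. This agrees with the Phase 2 text and Figure 2.
2. State one fixed time for the QLQ-C30 and one for the PEPPI, the same for all participants, with a short reason. If either is placed before the visit, amend the Phase 2 text and Figure 2 to match. In the congruence definition, state which time points are compared.
3. Check that Figure 3 shows the same order, and say in the Phase 2 text whether caregivers complete the questionnaires.
4. Record the completion time on each form.

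The cost is one sentence for the C-PSS, one each for the QLQ-C30 and the PEPPI, a clarification on caregivers, any matching edits, and a time field on the forms. No extra patients or staff are needed. Participants would answer 27 items after the visit if only the C-PSS is placed there, or 67 if all three are.
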